5.2 PROCEDURES BY VISIT

5.2.1 Visit 1: Screening (Day-28)

Patients are often pre-screened for the study. Pre-screening information is generally obtained through customary practice of routine medical intake for the patients. Of note, patients who have completed pre-screening are not pre-qualified for participation in the study, therefore the site is still responsible for completing all required screening assessments in accordance with the study protocol.

The patient must be screened, ideally, within 28 days before the randomization visit in the study. A 3-day window is allowed to complete the Day 1 visit. The last 14 days prior to randomization will be used as the patient's baseline electronic diary assessment.

The following will be completed at the Screening Visit:

- Obtain informed consent/assent. The patient must provide written assent and parent or caregiver must provide written informed consent.
- Assign a unique patient number. Unique patient numbers will begin with the clinical site number, eg, 001 followed by a 3-digit number. Unique patient numbers will be assigned sequentially by clinical site personnel accessing the EDC system. This unique patient number will be kept for the duration of the study. Patients who discontinue from the study before randomization will retain their unique patient number (ie, numbers from screen fail patients will NOT be reassigned).
- Assess willingness and ability to maintain a stable diet and fiber supplements (if applicable) for the study period and to comply with not using laxatives with the exception of the rescue medication provided as part of the study.
- Determine eligibility, based on Rome III criteria for child/adolescent functional constipation (**Appendix A**)
- Verify inclusion/exclusion criteria.
- Collect demographic information.
- Record medical history, including GI and bowel habit history.
- Record prior and concomitant medications and dietary history.
- Perform a physical examination, including measurement of body weight and height.
- Measure vital signs (seated blood pressure, heart rate, respiration, and body temperature).
- Perform urine screen for opioids (see **Section 4.3.2** for details).
- Perform a urine pregnancy test for female patients (a negative result must be confirmed at Screening and on Day 1 prior to randomization).
- Collect blood and urine samples for safety laboratory tests (serum chemistry, including thyroid-stimulating hormone [TSH], hematology, and urinalysis).
- Perform 12-lead ECG in the semi-recumbent position.

- Have the patient complete the Excessive Flatulence and Fecal Incontinence questionnaires (Per Study Procedure Manual).
- Train patients how to use the electronic diary to record their responses about BM and CIC-related symptoms and activate the diary.
- Distribute a laminated card with the BSFS to patients and explain how to use it to record stool consistency in their daily electronic diaries.
- Ensure patients understand the importance of entering data in their diaries on daily basis for all questions.
- Dispense rescue medication to patients and instruct them on the appropriate use.

Patients who fail to qualify for randomization during the Screening Period will be considered Screen Failures and the reason for failure will be documented.

Patients who screen-failed may be allowed to re-screen under certain circumstances upon review and approval by the Medical Monitor.

5.2.2 Visit 2: Randomization / Day 1 of Treatment Period

Study eligibility must be confirmed ***prior to randomization***, including the following:

- Confirm that patient has used only study-supplied rescue medication laxative (Dulcolax[®]) since Visit 1
- Urine drug screen (see **Section 4.3.2** for details)
- Urine pregnancy test, if applicable
- Update medical history and concomitant medications, as necessary

The last 14 days of daily diary entries prior to randomization will be used for determination of baseline data. Only patients who meet the protocol criteria for confirmation of CIC and demonstrate diary and RM compliance are eligible for randomization. This eligibility determination will include:

- A review of the baseline diary entries to ensure patients have completed at least 5 of the 7 days of diary entries in each of the 2 weeks of baseline assessments
- A review of the BM frequency data to ensure < 3 SBMs in each of the 2 weeks of the baseline diary assessment period
- A review of rescue medication use to ensure patients have not used RM for more than 2 days in each baseline week

The eligibility determination based on these criteria will be programmed into the IWRS and the system will report out eligibility (the PI or site staff will not be responsible for evaluating diary data to make the diary-based eligibility determination).

The following procedures will be performed ***only for patients eligible for randomization:***

Procedures ***prior to study drug dosing:***

- Physical examination (including body weight) and vital signs (seated blood pressure, heart rate, respiration, and body temperature)
- 12-lead ECG (semi-recumbent)
- Assess adverse events
- Safety laboratory assessments (hematology, serum chemistry, urinalysis)
- Confirm that patient is on a stable diet and has no significant changes in their consumption of liquids or fiber or their level of activity
- Blood samples for plecanatide/SP-338 concentration and immunogenicity assessments (see **Section 4.3.3** for details)
- Have the patient complete all baseline PRO questionnaires (Per Study Procedure Manual).

The first dose of study drug will be administered at the clinical site under supervision. The time of dosing will be recorded.

The following procedures will be performed ***after study drug dosing:***

- At selected sites and in a subgroup of patients who consented to an additional PK analysis, blood samples will be obtained for PK assessment 30, 60, 90 and 120 minutes after study drug administration
- At one hour post dosing, the patient will have a standard 12-lead ECG performed; clinically significant findings will be assessed as an adverse event
- Dispense 4-week supply of study drug with the instructions for use and storage (as described in **Section 6.3**)
- Distribute additional rescue medication (Dulcolax® tablets), if needed
- Re-emphasize the need for diary compliance, as necessary
- Confirm the next visit and explain the importance of meeting the 3-day window for completion of study visits

5.2.3 Visit 3: Week 4, Day 28 (± 3 days) of Treatment Period

The following will be completed at Visit 3:

- Collect/record unused study drug from the supply dispensed at the previous visit
- Review the electronic diary compliance reports and re-emphasize the need for diary compliance, as necessary
- Have the patient complete the PRO questionnaires (per Study Procedure Manual)

- Assess/record changes in concomitant medications and diet
- Physical examination (including body weight) and vital signs (seated blood pressure, heart rate, respiration, and body temperature)
- Safety laboratory assessments (hematology, serum chemistry, urinalysis)
- Collect blood samples for immunogenicity assessments
- Urine pregnancy test, if applicable
- Assess adverse events
- Dispense 4-week supply of study drug
- Distribute additional rescue medication (Dulcolax® tablets), if needed

5.2.4 Visit 4: Week 8, Day 56 (+ 3 days) of Treatment Period

The following will be completed at Visit 4:

- Collect/record unused study drug from the supply dispensed at the previous visit
- Review the electronic diary compliance reports and re-emphasize the need for diary compliance, as necessary
- Have the patient complete the PRO questionnaires (per Study Procedure Manual)
- Assess/record changes in concomitant medications and diet
- Physical examination (including body weight) and vital signs (seated blood pressure, heart rate, respiration, and body temperature)
- 12-lead ECG (semi-recumbent)
- Safety laboratory assessments (hematology, serum chemistry, urinalysis)
- Urine pregnancy test, if applicable
- Collect blood samples for plecanatide/SP-338 concentration and immunogenicity assessments
- Assess adverse events
- Distribute additional rescue medication (Dulcolax® tablets), if needed

5.2.5 Visit 5: Week 10, Day 70 (+ 3 days) – Posttreatment Follow-up (End of Study)

The following will be completed at Visit 5:

- Assess/record changes in physical examination, vital signs, concomitant medications and diet
- Perform urine pregnancy test, if applicable
- Assess adverse events
- Collect/record unused study drug, if not collected (per protocol) at Visit 4
- Have the patient complete the PRO questionnaires ((per Study Procedure Manual)

5.2.6 Early Withdrawal Visit (EW)

Patients are free to withdraw from participation in the study at any time. Investigators may choose to discontinue a patient's participation in the study if they believe it is in the patient's best interest clinically. If a patient's post-randomization compliance is of concern, contact the medical monitor to discuss. If the patient has an intervening illness that requires discontinuation of study participation, the patient and Investigator will follow procedures for early withdrawal. The following are examples of AEs that qualify for Early Withdrawal (EW):

- A positive pregnancy test will require discontinuation from the study (see **Section 7.7**).
- Changes in laboratory values, PE findings, or other assessments considered by the Investigator (or designee) to be clinically significant will require discontinuation from the study.
- Clinically significant TEAEs, including clinically significant laboratory test abnormalities or SAEs regardless of relatedness to study treatment that cause the patient, investigator, or Sponsor to feel it is not in the patient's best interest to continue.

A patient may also be withdrawn from study drug/study by the Sponsor, regulatory authorities, or the institutional review board (IRB). Patients will also be withdrawn if the entire study is terminated prematurely as described in **Section 9.10**.

Patients who discontinue early from the study should, if possible, have an Early Withdrawal Visit. The Investigator must make every effort (with proper documentation) to have the patient complete this final visit. This visit should take place as soon as possible (and within 5 days) after the patient stops taking study drug.

The following procedures will be performed at the Early Withdrawal Visit:

- Collect/record unused study drug from the supply dispensed at the previous visit
- Review the electronic diary compliance reports and re-emphasize the need for diary compliance, as necessary
- Have the patient complete the PRO questionnaires (see Study Procedure Manual)
- Assess/record changes in concomitant medications and diet
- Physical examination (including body weight) and vital signs (seated blood pressure, heart rate, respiration, and body temperature)
- 12-lead ECG (semi-recumbent)
- Safety laboratory assessments (hematology, serum chemistry, urinalysis)
- Perform urine pregnancy test, if applicable
- Collect blood samples for plecanatide/SP-338 and immunogenicity assessments
- Assess adverse events.
- Distribute additional rescue medication (Dulcolax® tablets), if needed

In all cases, a single, primary reason for withdrawal must be recorded on the eCRF.

The End of Study assessments should be performed 2 weeks following the last study drug administration. Patients withdrawn after randomization will **not** be replaced.

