6.4 BLINDING AND BREAKING THE BLIND

The study will be performed in a double-blind manner. All study drugs will be supplied in identical blister packs and tablets will be similar in color, smell, taste, and appearance, thereby assuring double-blind conditions.

In the event of a need to break the blind, the Investigator at the clinical site will have the ability to break the treatment code using the IWRS. The blind should only be broken following discussion on a case-by-case basis, with the Sponsor/Medical Monitor (except in a medical emergency). The Sponsor's Medical Monitor will also be granted emergency code-break privileges using the IWRS. All telephone calls resulting in an un-blinding event will be documented. The Sponsor and CRO, as applicable, will specify who in each company is able to review unblinded treatment in a blinded trial.

In the event of a treatment code-break, the time, date, reason, name, and signature of the person responsible for breaking the code must be fully documented in the patient's source documents and any associated AE recorded. The breaking of the blind will result in the withdrawal of the patient from study participation, and the patient should follow the procedures detailed for Early Withdrawal Visit study assessment (see **Section 5.2.6**).

The overall randomization code for the study will be broken at study completion. This will occur once all final clinical data have been entered into the database, data queries have been resolved, and the assignment of patients to the analysis sets has been completed.

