8.2 SAMPLE SIZE AND POWER CONSIDERATIONS

Based on data from two phase 3 trials conducted by the sponsor in adults with CIC, assume a mean change from baseline in weekly SBM rate for placebo-treated subjects of 1.2 with a standard deviation of 2.6; similarly, for plecanatide-treated subjects, assume a mean change from baseline of 3.1 with a standard deviation of 4.0. Then, a *t*-test for the difference in means of two independent samples with unequal variances, at a two-sided level of significance of 0.05 and 80% power to detect the assumed difference in means, would require 51 subjects per treatment group. Since study SP304202-13 is being conducted in adolescents with CIC, and the primary analysis of the primary endpoint will be an ANCOVA using a linear mixed-effects model, the sponsor believes that 30 subjects per treatment group (placebo and 3 dose levels of plecanatide), yielding a planned target enrollment of a total of 120 subjects, will prove sufficient for achieving the primary objective of this phase 2 study.

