8.3 ANALYSIS POPULATIONS

The following populations will be assessed:

Safety Population: All randomized patients who receive at least one dose of the study drug. Patients will be analyzed according to the treatment received. All safety analyses will be based on the Safety Population.

Intent-to-Treat (ITT) Population : All patients randomized to study treatment. Patients will be analyzed according to the treatment to which they are randomized. The ITT Population is the main population for assessments of efficacy.

Per Protocol (PP) Population: All patients in the ITT population who complete the 8-week Treatment Period or discontinue from study treatment due to adverse event(s) or lack of efficacy, with the exception of major protocol violators. Criteria to identify the PP population will be detailed in the SAP. Decisions regarding exclusion from the PP Population will be made prior to unblinding the database.

Efficacy analyses will be based on the ITT Population. Efficacy analyses will be repeated for the PP Population to assess the sensitivity of the analyses to the choice of analysis set.

Deviations from the study protocol, including violations of inclusion/exclusion criteria, will be assessed as “minor” or “major” in cooperation with the Sponsor. Major deviations from the protocol will lead to the exclusion of a patient from the PP Population and will be determined prior to unblinding the study database.

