8.8 EFFICACY ANALYSES

8.8.1 Primary Efficacy Endpoint

The primary efficacy endpoint is the proportion of responders for the last 2 weeks of the Treatment Period (responder = a child who experiences >3 SBMs per week for each of the last two weeks of the treatment period) compared to placebo and across treatment groups.

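### Diary follow-up is tied to the last dose, so patients who stop study drug by Day 41 have missing or partial Weeks 7–8 data, filled with zeros in the ITT analysis

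*Combined protocol and SAP*

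**What the plan says.** - **Timing after early stopping (5.2.6).** The Early Withdrawal visit is timed from the last dose: "This visit should take place as soon as possible (and within 5 days) after the patient stops taking study drug". The section describes it as the patient's final visit, yet goes on: "The End of Study assessments should be performed 2 weeks following the last study drug administration". Section 1 has patients keep the daily diary for two weeks after the last dose.
- **Code break (6.4).** "The breaking of the blind will result in the withdrawal of the patient from study participation".
- **Stopping rules (6.2, Table 4).** These discontinue study drug for listed events. They do not say whether the patient stays in the study. Section 5.2.6 refers to withdrawal from study drug and from the study in one breath.
- **Analysis set (8.3).** All randomized patients: "The ITT Population is the main population for assessments of efficacy".
- **Endpoint (8.8.1, 8.4.2).** A responder is "a child who experiences >3 SBMs per week for each of the last two weeks of the treatment period". Weeks 7 and 8 are Days 43–49 and 50–56.
- **Missing weeks (8.4.1).** A week without bowel movement data gets an SBM rate of 0, including all planned weeks remaining after withdrawal. Missing days within a week also count as 0. Stool consistency and symptom scores stay missing.
- **Primary analysis (8.8.1.1).** A mixed model of change in weekly SBM rate over all eight weeks.

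**The concern.** An ITT comparison needs the outcome in everyone randomized, at the time the endpoint is defined. Here the diary clock runs from the last dose, while the endpoint is fixed in calendar time from Day 1. No section keeps a patient who has stopped drug on the diary to Day 56.

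The gap is then closed with a value that can point the wrong way. A patient who stopped because of frequent loose stools is entered as having no SBMs, and that zero enters both responder status and the mixed model. If stopping differs between arms, the comparison depends on assigned values in the patients whose outcome is most related to treatment. A sensitivity analysis can vary those values, but it cannot recover the diary days.

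**Working it through.** **1. The plan's calendar.** For a completer the last dose is Day 56, and 56 + 14 = Day 70, which is Visit 5. The total is 28 + 56 + 14 = 98 days, as in Section 9.9. The rule of last dose + 14 days therefore reproduces the plan's own schedule.

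**2. Coverage of Days 43–56.** Let L be the day of the last dose, with the diary ending on Day L + 14. Days observed = max(0, min(56, L + 14) − 42).

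| Last dose | Days observed of 14 |
|---|---|
| Day 14 | 0 (diary ends Day 28) |
| Day 28 | 42 − 42 = 0 |
| Day 29 | 43 − 42 = 1 |
| Day 41 | 55 − 42 = 13 |
| Day 42 or later | 56 − 42 = 14 |

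Week 8 alone has max(0, min(56, L + 14) − 49) days, which is zero up to L = 35. A responder must qualify in both weeks, so under the zero rule a last dose by Day 35 means automatic non-response.

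If the diary ended at the Early Withdrawal visit instead (up to L + 5), there would be no window data up to Day 37 and full data only from Day 51.

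Weeks 9–10 are taken as Days 57–70, which the visit schedule implies although 8.4.2 lists only the treatment weeks. Days observed = max(0, L + 14 − 56): none for a last dose by Day 42, and 1 to 13 for Days 43–55.

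**3. Number of patients.** The plan states no dropout rate. Assume 5–15% stop early (6–18 of 120), spread evenly over Days 1–55. The shares are 28/55 = 51% with no window data, 13/55 = 24% partial and 14/55 = 25% complete.

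| Stop early | None | Partial | Complete |
|---|---|---|---|
| 6 of 120 | 3.1 | 1.4 | 1.5 |
| 18 of 120 | 9.2 | 4.3 | 4.6 |

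One patient is 1/30 = 3.3 percentage points of an arm's responder rate. With equal stopping across arms, the part of each arm's rate not fully observed is 41/55 × 5% = 3.7 points to 41/55 × 15% = 11.2 points.

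**4. Effect on the mixed model.** Section 8.2 says to "assume a mean change from baseline in weekly SBM rate for placebo-treated subjects of 1.2 with a standard deviation of 2.6" and, for plecanatide, to "assume a mean change from baseline of 3.1 with a standard deviation of 4.0", a difference of 1.9, "at a two-sided level of significance of 0.05 and 80% power to detect the assumed difference in means". The unequal-variance t-test has 80.3% power at 51 per group and 79.5% at 50, so the plan's 51 is reproduced. At the planned 30 per group, power is 57.1%.

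Suppose a fraction d of both arms had zeros for all eight weeks. Their change is then minus their baseline, and the difference becomes 1.9 × (1 − d). At d = 10% this is 1.71, with power of 47–49% at 30 per group (baseline of 1–2 SBMs per week assumed). With 10% on active and 5% on placebo it is 1.55–1.60, with power of 40–44%.

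These are ceilings, because stoppers also contribute observed weeks. Under even stopping the mean number of uncollected treatment days is (41 + 40 + … + 1)/55 = 861/55 = 15.7 of 56, or 28%. With equal stopping, the loss is then about 0.28 × d × 1.9: 0.03 SBMs per week at 5%, 0.05 at 10% and 0.08 at 15%. With 10% against 5%, the ceiling loss of 0.30–0.35 becomes about 0.08–0.10. Some of this is true loss of effect off drug, which observed diaries would also show.

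**The case against.** - **There is a missing-data rule.** Section 8.4.1 prespecifies the zero and labels it a worst case. Counting early leavers as failures is a recognised choice for a responder endpoint, and using off-drug diary data changes the question being estimated. This stands as a reason to keep the zero rule as a stated analysis. It is no reason to leave the data uncollected, since with the diary in hand both questions can be answered.
- **Never collected.** A reader might infer that Weeks 7–8 are lost for every early stopper. The two-week tail covers the window in full from a last dose on Day 42 and in part for Days 29–41. Likewise, Weeks 9–10 are wholly uncovered only for a last dose by Day 42.
- **Stopping drug ends participation.** A reader might infer this as a general rule. Section 6.4 states it for code breaks only. Section 6.2 stops treatment and is silent on study status, and 8.3 speaks of discontinuing study treatment. At the Early Withdrawal visit, sites are still told to stress diary compliance. Leaving after a Table 4 stop is implied because 5.2.6 gives no other path, but it is not stated.
- **Treatment-related stopping.** The adult dose-ranging study in 2.1.4 reports diarrhea withdrawals of 3% at 3.0 mg against 0.4% on placebo. That dose is twice this trial's highest, so the figures are context only. Section 6.2 does warn of possibly higher pediatric risk.
- **The responder rate is not what 8.8.1.1 models.** This is correct. The mixed model uses all eight weeks, and step 4 shows a small loss there when stopping is balanced.
- **Limited recovery.** Patients who withdraw consent or assent, or who are withdrawn for diary non-compliance (8.6), would yield little more data.

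**Conclusion.** The concern holds in a bounded form. Follow-up is anchored to the last dose, stopping drug and leaving the study are not separated, and no section provides for the diary to reach Day 56 after an early stop. By design, a last dose by Day 28 leaves no endpoint-window data and one on Days 29–41 leaves 1–13 days.

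Under the assumed 5–15% early stopping, spread evenly, about 3–9 of 120 patients have no window data and 1–4 have partial data. The coverage days follow from the plan's own calendar. The patient counts rest on the two assumptions: stopping concentrated in the first four weeks would raise the number with no data, and late stopping would lower it. The consequence is larger for the responder endpoint than for the eight-week mean, and larger again if stopping differs by arm, which the documents cannot settle. In an exploratory trial of 30 per arm this is worth correcting because the change is cheap and the lost diary days cannot be recovered afterwards.

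**What to change.** 1. In 5.2.6 and 6.4, with a cross-reference from 6.2, define discontinuation of study drug and withdrawal from the study as separate events. Leave every stopping and rescue rule as it is.
2. Patients who stop drug for any reason, including after a code break, and do not withdraw consent or assent complete the Early Withdrawal visit and the two-week End of Study safety assessments. They continue the eDiary to Day 56, ideally Day 70. Record any laxative use with date and time, so that SBM status can be derived.
3. Reconcile the description of the Early Withdrawal visit as final with the later End of Study assessments.
4. Use the observed weeks in the ITT SBM and responder analyses. Keep the 8.4.1 zero/non-responder rule for weeks still missing. Report as a sensitivity analysis one that scores all weeks after drug stop as zero or non-response.
5. Summarize drug discontinuation and study withdrawal separately in 8.5 and 8.10. At present 8.5 covers discontinuation from the Treatment Period, and 8.10 counts only AEs leading to withdrawal from study participation.

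Cost: protocol and assent wording, plus a small change to the diary script, which now asks only about Dulcolax. The diary already runs to Day 70 for completers. Patients off drug carry some extra diary burden, and some will decline.
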